3.4 Randomization and Blinding

This is an open-label study. No blinding is needed. Subjects will be enrolled into cohorts based on cancer type; no randomization will be conducted.

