9 ADVERSE EVENTS/ SERIOUS ADVERSE EVENTS AND REPORTING

9.1 Adverse Events

An AE is defined as any unfavorable and/or unintended sign (including an abnormal laboratory finding), symptom, or disease temporally associated with the use of an IMP, whether or not related to the IMP.

All AEs within the reporting period (as defined below) are to be recorded in the AE eCRF. Nonserious AEs prior to initiation of study treatment will be recorded as medical history. Whenever possible, it is preferable to record a diagnosis as the AE term rather than a series of terms relating to a diagnosis.

The reporting period for AEs is as follows:

- After the ICF is signed but prior to the initiation of study treatment, only SAEs will be reported
- After the ICF is signed and the first administration of study drug, all nonserious AEs and SAEs are reportable and continue to be reported up to 30 days after the last dose of study drug
- During the Follow-up Period, AE reporting is limited to irAEs, AEs \geq Grade 3, and SAEs occurring up to 90 days after last dose of study drug

After the defined AE reporting period, all SAEs assessed as related to study treatment will be reported to the Sponsor. At the last scheduled visit, the Investigator must instruct each subject to report to the Investigator and/or Sponsor or designee, any subsequent SAE that the subject's personal physician(s) believes might be related to prior study treatment. The Investigator must notify the study Sponsor or designee of any death or SAE that may have been related to prior study treatment.

For this Module, disease progression is an efficacy endpoint and in and of itself is not considered an AE or SAE unless disease progression results in death. Death that occurs during the AE reporting period (as defined above), that is attributed solely to disease progression of the

condition, will be recorded in the AE eCRF as a Grade 5 AE (regardless of attribution to study treatment). Deaths reported as SAEs due to progressive disease and considered not related to study treatment will be excluded from TEAE analysis.

All AEs (including SAEs), whether or not related to study drug, must be fully and completely documented using precise medical terminology in the applicable eCRFs (eg, AE eCRF, drug dispensation eCRF).

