9.2 Adverse Event Classification

9.2.1 Relationship to Investigational Drug

The Investigator’s assessment of causality must be provided for all AEs, serious and nonserious and recorded in the AE eCRF. The causality of each AE should be assessed and classified by the Investigator as “related” or “not related.” An AE is considered related if there is “a reasonable possibility” that the AE may have been caused by the study drug (ie, there are facts, evidence, or arguments to suggest possible causation). Several factors should be considered in making this assessment, including:

- Temporal relationship of the AE to the administration of study drug(s)/study procedure
- Whether alternative etiology can be identified that could cause AE
- Mechanism of action of the study drugs
- Biological plausibility

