9.6.1 Investigator Reporting to the Sponsor

All SAEs that occur after the ICF is signed and up to 90 days after administration of the last dose of study drug must be recorded in the AE eCRF within 24 hours of knowledge of the occurrence (this refers to any AE that meets any of the criteria in [Section 9.1.1](#), regardless if it is considered related to study drug). SAEs occurring more than 90 days after the last dose of study drug must be reported only if assessed as related to study drug.

To report the SAE, the Investigator must record the relevant information in the AE eCRF and any other applicable information in the relevant eCRF (eg, drug dispensation eCRF, applicable laboratory eCRF). If the event meets serious criteria and it is not possible for the site to access the EDC system, the site must complete the paper SAE reporting form and email or fax it to ICON Safety using the email or fax number listed in Table 8, all within 24 hours of awareness. When the EDC system becomes available, the site must enter the SAE information into the EDC, exactly as it was recorded on the paper SAE reporting form, within 24 hours of the system becoming available.

For all SAEs, the Investigator is obligated to obtain and provide information to the Sponsor and ICON Safety in accordance with the time frames for reporting specified above. In addition, an Investigator may be requested by the Sponsor to obtain specific additional follow-up information in an expedited fashion. This information may be more detailed than that captured in the AE eCRF or back-up paper SAE form. In general, this will include a description of the AE in sufficient detail to allow for a complete medical assessment of the case and an independent determination of possible causality. Information on other possible causes of the event, such as concomitant medications and illnesses, must be provided. In the case of a subject death, a death certificate and summary of available autopsy findings (as applicable) must be submitted as soon as possible to the Sponsor or its designee.

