9.8 Module-specified Events

Subjects with advanced cancer enrolling in this study who have received prior treatment may have some degree of bone marrow suppression from prior therapy and/or laboratory abnormalities due to underlying disease status. Only changes in the grade of baseline laboratory values that require intervention (eg, transfusions, delay in study treatment administration) should be reported as AEs.

For this protocol, disease progression is an efficacy endpoint and in and of itself is not considered an AE or SAE unless disease progression results in death. Death that occurs during the AE reporting period (as defined above) that is attributed solely to disease progression of the condition will be recorded in the AE eCRF as a Grade 5 AE (regardless of attribution to study

treatment). Deaths reported as SAEs due to progressive disease and considered not related to study treatment will be excluded from TEAE analysis.

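### The fatal-TEAE rate leaves out deaths judged due to progression and unrelated, so it depends on unblinded attribution and can only equal or fall below the all-cause rate

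*Combined protocol and SAP*

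**What the plan says.** Section 9.1 defines an AE without reference to causality: any sign, "symptom, or disease temporally associated with the use of an IMP, whether or not related to the IMP". Disease progression is treated as an efficacy endpoint and not as an AE, except where it leads to death. A death in the AE reporting period that is put down solely to progression "will be recorded in the AE eCRF as a Grade 5 AE (regardless of attribution to study treatment"). The next sentence takes a subset of these deaths out of the analysis: "Deaths reported as SAEs due to progressive disease and considered not related to study treatment will be excluded from TEAE analysis". Section 9.8 repeats the rule ("Deaths reported as SAEs due to progressive disease and considered not related" and so on), so it is not a stray line.

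On who judges, section 9.2.1 says "The causality of each AE should be assessed and classified by the Investigator as" related or not related. Section 3.4 says "This is an open-label study. No blinding is needed" and, of allocation, "no randomization will be conducted". The AE reporting period for SAEs runs to 90 days after the last dose.

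Section 10.2 places the safety methods in the Core and announces a separate SAP that overrides the Module where they differ. Neither is in the text available for review.

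**The concern.** Safety and tolerability is a secondary objective in both parts. The study rationale (section 1.4) expects better tolerability than earlier checkpoint combinations and refers to historical controls. There is no concurrent control, so a reported rate can be interpreted only if it is clear what was counted.

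The exclusion adds a causality filter that the AE definition does not contain. The filter rests on two judgements made with treatment known: that progression caused the death, and that study treatment did not. The Module gives the relatedness call to the investigator. It does not say who decides that a death is due to progression, or on what evidence. The recording sentence speaks of deaths attributed solely to progression. The exclusion sentence has no such qualifier, so it could be read to reach deaths where progression was only part of the cause.

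Such deaths are foreseeable in Part A. Under section 6.1, the first RECIST progression resets the baseline and is noted as immune-related stable disease, so a subject may still be on treatment when the disease has already grown by RECIST. If the TEAE table is the only place where fatal events are summarised, a reader cannot see how many deaths were removed or how much the figure depends on the attribution.

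**Working it through.** **No figure to reproduce.** The documents state no fatal-TEAE rate, expected number of deaths, misattribution rate or precision target for safety. The counts below are assumptions chosen for scale. The sample sizes are from the Module: n=40 is Cohort A2 Stage 1 (section 3.3), and 162 is the maximum total (section 3.2).

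**Step 1: comparison with the all-cause rate.** Let D be all deaths in the AE window, X those judged both due to progression and unrelated, and N the number treated.

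Reported rate = (D − X)/N ≤ D/N, because X ≥ 0.

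The reported rate is therefore equal or lower, whatever the quality of the attribution. With exact (Clopper-Pearson) 95% intervals, whose limits are the 0.025 quantile of Beta(x, N−x+1) and the 0.975 quantile of Beta(x+1, N−x):

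| N | D (assumed) | X (assumed) | All-cause D/N | Reported (D−X)/N |
|---|---|---|---|---|
| 40 | 1 | 1 | 1/40 = 2.5% (0.1 to 13.2) | 0/40 = 0% (0 to 8.8) |
| 40 | 2 | 2 | 2/40 = 5.0% (0.6 to 16.9) | 0/40 = 0% (0 to 8.8) |
| 40 | 4 | 2 | 4/40 = 10.0% (2.8 to 23.7) | 2/40 = 5.0% (0.6 to 16.9) |
| 40 | 8 | 6 | 8/40 = 20.0% (9.1 to 35.6) | 2/40 = 5.0% (0.6 to 16.9) |
| 162 | 16 | 8 | 16/162 = 9.9% (5.8 to 15.5) | 8/162 = 4.9% (2.2 to 9.5) |

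**Step 2: comparison with deaths not due to progression.** Let T be deaths not due to progression and P progression deaths. Let a be the share of T wrongly classed as progression and unrelated, and b the share of P that escapes exclusion.

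Expected reported count = T(1 − a) + P·b, against a target of T.

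Take N=40, T=2, P=6, so the target is 2/40 = 5.0%:

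| a | b | Count | Rate | Against 5.0% |
|---|---|---|---|---|
| 0 | 0 | 2 + 0 = 2 | 5.0% | equal |
| 0.25 | 0 | 1.5 + 0 = 1.5 | 3.75% | lower |
| 0 | 0.25 | 2 + 1.5 = 3.5 | 8.75% | higher |
| 0.25 | 0.25 | 1.5 + 1.5 = 3.0 | 7.5% | higher |

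The sign is that of P·b − T·a. The documents give none of these four quantities, so the direction cannot be settled.

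**Step 3: what the rule leaves in place.** A death attributed to progression but judged related does not meet both conditions and stays in the TEAE analysis. An excluded death remains in the AE eCRF. It also counts in OS, a secondary endpoint for Part A that section 2.2.1 lists for Part B as well. The exclusion applies to the death; no text removes the subject's other events. Section 9.7 has irAEs recorded as AESIs irrespective of causality, and section 10.2 names AESI frequency as an endpoint.

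**The case against.** A reader might infer more: that the fatal-TEAE rate is biased downward outright, that the investigator alone decides what is removed, and that treatment deaths drop out of sight. The documents do not support this.

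- *Direction.* Downward is certain only against the all-cause rate. The plan can be read as aiming at deaths not due to progression, since it treats progression as an efficacy outcome. Against that target, Step 2 shows that the error can go either way.
- *Who decides.* The Module does not name who attributes a death to progression. Section 9.6.1 asks for SAE reports in enough "detail to allow for a complete medical assessment of the case and an independent determination of possible causality", with a death certificate and any autopsy summary. This is not tied to the exclusion and no adjudication procedure is set out, but it does not leave everything to one judgement either.
- *Visibility.* The deaths stay in the eCRF and in OS, irAEs stay among the AESIs, and the DSMB reviews all safety information (section 3.5). A difference between database and table that comes from a prespecified filter is traceable and is not an inconsistency.
- *Comparators.* The historical safety figures in sections 1.1 and 1.2 are Grade 3 or 4 rates, mostly treatment-related. Removing unrelated deaths does not change the trial's corresponding rates.
- *Unseen text.* The Core or the SAP may already plan a table of all deaths.

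Most of this stands and limits the point. It does not remove it: OS does not show why a subject died, DSMB review does not determine what the final table reports, and the exclusion is stated twice in the Module without a companion total.

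**Conclusion.** The point holds in a limited form. The fatal-TEAE rate as defined depends on unblinded attribution in an uncontrolled study with no described adjudication, and it cannot exceed the all-cause fatal-TEAE rate. Whether it over- or understates deaths not due to progression is unknown.

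The size cannot be computed from the documents. The illustrations rest on assumed counts. At n=40, each restored death adds 1/40 = 2.5 percentage points, so the gap is small if few progression deaths fall in the window and large if many do. There is no between-arm bias because there is no comparator arm, and neither ORR nor pathologic response is touched. This is a worthwhile, inexpensive improvement to a secondary safety result. It does not threaten the trial's main conclusions. It assumes that neither the Core nor the SAP already provides the all-deaths summary.

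**What to change.** Replace the exclusion sentence in sections 9.1 and 9.8, and make the same change in the SAP, since it supersedes the Module. Possible wording: *All Grade 5 events in the AE reporting period are tabulated by cause and by relationship to study treatment. Deaths judged to result from progression and to be unrelated appear on a separate line, and the fatal-TEAE total is presented both including and excluding them.*

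In the same place, state who attributes a death to progression and on what evidence, and whether the exclusion is limited to deaths attributed solely to progression.

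The cost is one extra table line and, where such deaths occur, a less favourable all-cause figure beside the filtered one. No new data are needed, because these deaths are already in the AE eCRF. The limit should be understood: a toxicity death wrongly called progression would still be mislabelled, but it would be counted and visible.

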9.1.1 Serious Adverse Events

An SAE is any untoward medical occurrence with any of the following outcomes:

- Death
- Life-threatening: An AE is considered “life-threatening” if, in the view of either the Investigator or Sponsor, its occurrence places the subject at immediate risk of death. It does not include an AE that, had it occurred in a more severe form, might have caused death.
- Requires or prolongs inpatient hospitalization
 - Note: examples of visits to a hospital facility that do not meet the seriousness criteria for hospitalization include outpatient surgery, preplanned or elective procedures, protocol-specified procedures (eg, administration of study drug)
- A persistent or significant incapacity or substantial disruption of the ability to conduct normal life functions
- A congenital anomaly/birth defect in the child or fetus of a subject exposed to the investigational product prior to conception or during pregnancy
- An important medical event, based on medical judgement, may jeopardize the subject or may require medical or surgical intervention to prevent one of the outcomes listed above (eg, anaphylaxis, allergic bronchospasm requiring intensive treatment in an emergency room or at home, blood dyscrasias, or convulsions that do not result in inpatient hospitalization)

9.1.2 Unexpected Adverse Events

An AE is considered “unexpected” if either of the following occur:

- If the event is not listed in the IB or is not listed at the specificity or severity that has been observed
- If an IB is not required or available, the event is not consistent with the risk information described in the general investigational plan or elsewhere in the clinical trial application, as amended

For example, under this definition, hepatic necrosis would be unexpected (by virtue of greater severity) if the IB referred only to elevated hepatic enzymes or hepatitis. Similarly, cerebral thromboembolism and cerebral vasculitis would be unexpected (by virtue of greater specificity) if the IB listed only cerebral vascular accidents.

“Unexpected,” as used in this definition, also refers to AEs or suspected adverse reactions that are mentioned in the IB as occurring with a class of drugs or as anticipated from the pharmacological properties of the drug, but are not specifically mentioned as occurring with the particular drug under investigation. For this Module, unexpectedness will be determined by the Sponsor using the IB as a reference.

For ipilimumab, refer to the current local prescribing information (eg, US package insert Sections 5 and 6 or European Medicines Agency summary of product characteristics Section 4.8) for reference safety information and other information pertaining to AEs associated with ipilimumab treatment.

9.2 Adverse Event Classification

9.2.1 Relationship to Investigational Drug

The Investigator’s assessment of causality must be provided for all AEs, serious and nonserious and recorded in the AE eCRF. The causality of each AE should be assessed and classified by the Investigator as “related” or “not related.” An AE is considered related if there is “a reasonable possibility” that the AE may have been caused by the study drug (ie, there are facts, evidence, or arguments to suggest possible causation). Several factors should be considered in making this assessment, including:

- Temporal relationship of the AE to the administration of study drug(s)/study procedure
- Whether alternative etiology can be identified that could cause AE
- Mechanism of action of the study drugs
- Biological plausibility

9.2.2 Severity

The severity of an AE describes the degree of impact upon the subject and/or the need for and extent of medical care necessary to treat the event.

AE grading will be defined by CTCAE Version 5.0. If the CTCAE Version 5.0 does not apply, the severity descriptions in [Table 7](#) will be used to determine the severity of the AE.

Table 7 Adverse Event Severity

Grade	Description
Grade 1	Mild; asymptomatic or mild symptoms; clinical or diagnostic observations only; intervention not indicated
Grade 2	Moderate; minimal, local or noninvasive intervention indicated; limiting age-appropriate instrumental activities of daily living
Grade 3	Severe or medically significant but not immediately life-threatening; hospitalization or prolongation of hospitalization indicated; disabling; limiting self-care activities of daily living
Grade 4	Life-threatening consequences; urgent intervention required
Grade 5	Death related to an adverse event

9.3 Exposure In Utero

Subjects will be instructed to notify the Investigator if the subject or subject's partner becomes pregnant during the study or within 6 months after the last dose of study drug. The Investigator must notify the Sponsor within 24 hours via the Pregnancy Notification Form (preferred). If it is not possible to report the pregnancy via the Pregnancy Notification Form, telephone or email will be acceptable to meet the 24-hour reporting requirement. The Investigator should obtain informed consent/assent from the subject or subject's partner allowing the Investigator to obtain information regarding the pregnancy and its outcome. If the subject or subject's partner provides informed consent/assent, the Investigator should follow the pregnancy until outcome. A final Pregnancy Notification Form should be completed and submitted to the Sponsor when the outcome of the pregnancy is known.

If the outcome of the pregnancy meets the criteria for immediate classification as an SAE (eg, spontaneous abortion, elective abortion, or birth defect), the Investigator should follow the procedures for reporting an SAE.

9.4 Monitoring of Adverse Event Data

Individual subject safety will be assessed by the Investigator on an ongoing basis. AE data will be monitored and reviewed at regular intervals by the Sponsor to assess for any emerging safety signals or trends.

AEs occurring during the reporting period (defined in [Section 9.5](#)) should be followed until resolution to baseline status, stabilization, or initiation of a new anticancer therapy.

Proper instruction regarding AESIs will be provided to each site to ensure prompt reporting and communication between the Sponsor, Investigators, the US Food and Drug Administration (FDA), and other applicable regulatory agencies or health authorities.

For SAEs, the Investigator must complete the SAE form electronically in the electronic data capture (EDC) system for the study with as much information as possible and submit it within the time frame described in [Section 9.6](#). When new significant information is obtained, as well as when the outcome of an event is known, the Investigator should record the information in the

EDC system, as applicable. If the subject was hospitalized, a copy of the discharge summary and any other relevant hospital records (eg, admission report, laboratory test results, etc.) should be included as part of the subject medical file.

All AEs considered to be related (definitely, probably, or possibly related) to study drug and all SAEs will be followed until resolved or until a stable status has been achieved. The type of follow-up (eg, phone, site visit, etc.) will be left to the discretion of the Investigator.

9.5 Documentation of Adverse Events by Investigator

Subjects will be evaluated and questioned generally to identify AEs during the course of the study. Any nonserious AEs occurring after signing the ICF and prior to administration of the first dose of study drug will be recorded in the medical history eCRF. Events occurring after administration of the first dose of study drug will be recorded in the AE eCRF. AEs that occur up to 30 days after administration of the last dose of study drug must be reported as AEs in the EDC system. Additionally, all irAEs, AEs \geq Grade 3, and SAEs that occur up to 90 days after administration of the last dose of study drug must be reported in the EDC system. See also [Section 9.6](#) for reporting of SAEs.

All AEs spontaneously reported by the subject and/or in response to an open question from study personnel or revealed by observation, physical examination, or other diagnostic procedures will be recorded in the AE eCRF. Wherever possible, a specific disease or syndrome rather than individual associated signs and symptoms should be identified. However, if an observed or reported sign or symptom is not considered a component of a specific disease or syndrome by the Investigator, it should be recorded as a separate AE.

Any clinically relevant deterioration in laboratory assessments or other clinical findings is considered an AE and must be recorded in the AE eCRF. Clinical syndromes associated with laboratory abnormalities are to be recorded as appropriate (eg, diabetes mellitus rather than hyperglycemia). In addition, an abnormal test finding will be classified as an AE if 1 or more of the following criteria are met:

- The test finding is accompanied by clinical symptoms
- The test finding necessitates additional diagnostic evaluation(s) or medical/surgical intervention; including significant additional concomitant drug treatment or other therapy.
Note: Simply repeating a test finding, in the absence of any of the other listed criteria, does not constitute an AE
- The test finding leads to a change in study drug dosing or discontinuation of subject participation in the clinical research study
- The test finding is considered an AE by the Investigator

If an abnormal laboratory value is recorded as an AE, then the corresponding laboratory value must be marked clinically significant in the EDC system. Similarly, if an abnormal laboratory value is marked clinically significant in the EDC system, it should be recorded as an AE.

Wherever possible, a specific disease or syndrome rather than individual associated signs and symptoms should be identified. However, if an observed or reported sign or symptom is not considered a component of a specific disease or syndrome by the Investigator, it should be recorded as a separate AE. Laboratory data are to be collected as stipulated in this Module and the Core ([Appendix A](#)). Clinical syndromes associated with laboratory abnormalities are to be recorded as appropriate (eg, diabetes mellitus rather than hyperglycemia).

[figure not shown]
